15.2.3 AE expectedness

It is sponsor's responsibility to evaluate expectedness of each device-related AE in accordance with sponsor's standard operating procedure (SOP). Expectedness is categorized as either:

- *Expected.* AE is consistent with the risk information described in the ICF, IFU and clinical investigational protocol (see Section 16); or
- *Unanticipated or unexpected.* AE is considered UADE or USADE if it is not consistent with the risk information described in the ICF, IFU and clinical investigational protocol (see Section 16).

15.3 AE Adjudication

AEs are reviewed by the sponsor on a regular, ongoing basis. Each AE will be reviewed by sponsor in accordance with the sponsor's SOP. The study sponsor is responsible for ensuring that all AEs are appropriately recorded, adjudicated and, when applicable, reported to government(s),

ethics committee(s) and other study sites, per applicable regulations. The following is reviewed for each AE:

- Need for clarification or additional information from the site
- Appropriateness of classifications for severity, causality and expectedness
- If the adverse event is unanticipated, determination as to whether it poses unreasonable risk of harm to study subjects if it were to reoccur; and
- Requirements for reporting to the FDA and site IRB based on the nature of the event.

Outputs of reviews are filed by sponsor, and action items are tracked to resolution.

If the investigator and sponsor do not agree on the seriousness or causality of an event, the event will be reviewed by an independent adjudicator, who is a qualified medical expert. The adjudicator is blinded to treatment assignment and will have access to the following:

- AE information reported in the EDC system
- A list of potential risks associated with the implant device, implant procedure, explant procedure and stimulation therapy
- Information provided by investigators, including clinical notes, laboratory results, concomitant medications, and medical/surgical history; and
- Clinical outcome measures reported in the EDC system.

The independent adjudicator may request further information if this is required to complete AE review. The adjudicator will confirm their determination of seriousness and causality of the event. The adjudicator's decision is considered as final and is recorded in the EDC system and used in all analyses.

In accordance with the DMC Charter, all AEs are reviewed by the DMC on an ongoing, regular basis, with *ad-hoc* reviews occurring within 5 working days of sponsor notification of any subject death or SAE related to the implant procedure, explant procedure, implant device, or stimulation. The DMC review meetings and recommendations will be documented in meeting minutes and filed in accordance with the DMC Charter.

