15 ASSESSMENT OF SAFETY

15.1 Specifications of Safety Parameters

Adverse events (AEs) for each subject from the time the subject gives written informed consent through Week 264 (end of study) will be recorded in the EDC system and monitored. Each AE will be evaluated by clinical investigators in terms of seriousness, severity (i.e., mild, moderate, severe) and strength of relationship (i.e., not related, unlikely related, probably related, definitely related, indeterminate) to the implant device, implant procedure, explant procedure, Energizer and stimulation therapy. Each AE will be reviewed by sponsor in accordance with sponsor's SOP. The study sponsor is responsible for ensuring that all AEs are appropriately recorded, adjudicated and, when applicable, reported to the government(s), ethics committee(s) and other study centers per applicable regulations. The sponsor will also appoint an independent Data Monitoring Committee (DMC) for ongoing monitoring of subject safety (see Section 18.2.5). Subjects with RA experience a persisting set of symptoms associated with the disease and may continue to present with a wide range of symptoms during the recovery process after the implant procedure. Subjects healing appropriately may suffer from acute infections and/or inflammatory exacerbations unrelated to the procedure due to the natural course of their RA. Therefore, clinical investigators will evaluate the occurrence of AEs, excluding usual post-operative recovery signs and symptoms experienced by study subjects, unless corroborated by objective findings and/or requiring specific medical or therapeutic interventions (e.g., antibiotics).

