15.2.2 AE causality

The relationship of all AEs to the implant procedure, explant procedure, implant device, Energizer and stimulation will be evaluated by Co-PIs and categorized as:

- *Definitely related.* There is a clear temporal association, and no other possible cause.
- *Probably related.* There is a clear temporal association, and a potential alternative etiology is not apparent.
- *Unlikely related.* The AE does not follow a reasonable temporal association; or causal relationship with the device or procedure involved in the research is unlikely but cannot be completely ruled out.
- *Not related.* The AE is completely independent of the study investigational device, and/or evidence exists that the event is definitely related to another etiology. There must be an alternative, definitive etiology documented by the investigator.
- *Indeterminate.* Information gathered about the AE is not sufficient to arrive at a definite conclusion about causal relationship.

Any AE that is determined to be definitely related or probably related to the study investigational device or procedure will be categorized as device related. Once the study dataset is locked for primary analysis and the study is unblinded, if a subject was assigned to the control group but has an AE reported as related to stimulation, the AE relationship will be updated to “not related.”

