16.6 Risk Analysis of the SetPoint System

For this pivotal study, a cross-functional team at SetPoint Medical performed a systematic risk analysis in accordance with BS EN ISO 14971:2012 to identify foreseeable sequences of events that could lead to hazardous situations when using the SetPoint System. These situations were then correlated to potential harms. Additional reasonably foreseeable harms beyond those identified above include:

- Electrocution caused by malfunction or misuse of Energizer or Wireless Charger;
- Critical tissue damage caused by a malfunction of Energizer that results in unsafe radio frequency exposure or a burn;
- Critical tissue damage caused by a malfunction of Energizer that results in delivery of unsafe stimulation levels;
- Critical tissue damage caused by damage to the implant;
- Asphyxiation caused by misuse of Energizer;
- Stroke caused by the implant migrating and obstructing a blood vessel;
- Death due to radio frequency emissions interference between the SetPoint system and some other life-sustaining equipment; and
- Catastrophic failure of the battery causing harm or severe injury, including death.

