18.2.5 Data Monitoring Committee

The sponsor will appoint an independent DMC to ensure compliance and proper clinical study monitoring. The DMC will be responsible for safeguarding the interests of study subject, assessing the safety and efficacy of the interventions during the trial, and for ongoing monitoring of the overall conduct of the study. During Stage 1 enrollment, the DMC will meet after enrollment of 15, 30, 45, and 60 subjects. During Stage 2 enrollment, the DMC will meet once every 3 months. Following completion of Stage 2 enrollment, the DMC will meet once every 6 months.

The DMC will provide recommendations about stopping or continuing the study based on their ongoing review of cumulative safety and efficacy data and at the end of Stage 1 based on a formal interim analysis of the Week 12 safety and efficacy data (see Section 17.3).

Early termination considerations will generally apply only to emerging safety issues of major concern, or problems with trial conduct that suggest the trial could not be completed successfully with a reliable conclusion in a feasible time frame. To contribute to enhancing the integrity of the trial, the DMC may also formulate recommendations relating to improving adherence to protocol-specified regimens and retention of participants, and the procedure for data management and quality control. The responsibilities of the DMC are further detailed in the DMC Charter.

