Subjects with explanted implant	xxx (xx.x%)	xxx (xx.x%)	xxx (xx.x%)
Unknown	xxx (xx.x%)	xxx (xx.x%)	xxx (xx.x%)
Other	xxx (xx.x%)	xxx (xx.x%)	xxx (xx.x%)

[1] Percentage calculated based on ITT Population.

Reference: Listing 16.xx.x

SOURCE:xxxxx SAS 9.4 {program location} {run date/time}

Table 14.1.3.1
Adverse Events
(Safety Population)

Variable	Treatment (N=xxx)		Control (N=xxx)		All (N=xxx)	
	Events	n (%)	Events	n (%)	Events	n (%)
Any AE	xx	xx (xx.x%)	xx	xx (xx.x%)	xx	xx (xx.x%)
Not Related	xx	xx (xx.x%)	xx	xx (xx.x%)	xx	xx (xx.x%)
Implant Procedure	xx	xx (xx.x%)	xx	xx (xx.x%)	xx	xx (xx.x%)
Implant Device	xx	xx (xx.x%)	xx	xx (xx.x%)	xx	xx (xx.x%)
Stimulation	xx	xx (xx.x%)	xx	xx (xx.x%)	xx	xx (xx.x%)
Explant Procedure	xx	xx (xx.x%)	xx	xx (xx.x%)	xx	xx (xx.x%)
Related [1]						
Implant Procedure	xx	xx (xx.x%)	xx	xx (xx.x%)	xx	xx (xx.x%)
Implant Device	xx	xx (xx.x%)	xx	xx (xx.x%)	xx	xx (xx.x%)
Stimulation	xx	xx (xx.x%)	xx	xx (xx.x%)	xx	xx (xx.x%)
Explant Procedure	xx	xx (xx.x%)	xx	xx (xx.x%)	xx	xx (xx.x%)
Indeterminate						
Implant Procedure	xx	xx (xx.x%)	xx	xx (xx.x%)	xx	xx (xx.x%)
Implant Device	xx	xx (xx.x%)	xx	xx (xx.x%)	xx	xx (xx.x%)
Stimulation	xx	xx (xx.x%)	xx	xx (xx.x%)	xx	xx (xx.x%)
Explant Procedure	xx	xx (xx.x%)	xx	xx (xx.x%)	xx	xx (xx.x%)
AE resulting in discontinuation	xx	xx (xx.x%)	xx	xx (xx.x%)	xx	xx (xx.x%)
AE by maximum severity						
Mild	xx	xx (xx.x%)	xx	xx (xx.x%)	xx	xx (xx.x%)
Moderate	xx	xx (xx.x%)	xx	xx (xx.x%)	xx	xx (xx.x%)
Severe	xx	xx (xx.x%)	xx	xx (xx.x%)	xx	xx (xx.x%)
Implant Procedure AE by maximum severity						
Mild	xx	xx (xx.x%)	xx	xx (xx.x%)	xx	xx (xx.x%)
Moderate	xx	xx (xx.x%)	xx	xx (xx.x%)	xx	xx (xx.x%)

CONFIDENTIAL

118 of 158

May not be reproduced outside of SetPoint Medical without written permission from Document Control.

Variable	Treatment (N=xxx)		Control (N=xxx)		All (N=xxx)	
	Events	n (%)	Events	n (%)	Events	n (%)
Severe	xx	xx (xx.x%)	xx	xx (xx.x%)	xx	xx (xx.x%)
Implant Device AE by maximum severity						
Mild	xx	xx (xx.x%)	xx	xx (xx.x%)	xx	xx (xx.x%)
Moderate	xx	xx (xx.x%)	xx	xx (xx.x%)	xx	xx (xx.x%)
Severe	xx	xx (xx.x%)	xx	xx (xx.x%)	xx	xx (xx.x%)
Stimulation AE by maximum severity						
Mild	xx	xx (xx.x%)	xx	xx (xx.x%)	xx	xx (xx.x%)
Moderate	xx	xx (xx.x%)	xx	xx (xx.x%)	xx	xx (xx.x%)
Severe	xx	xx (xx.x%)	xx	xx (xx.x%)	xx	xx (xx.x%)
Explant Procedure AE by maximum severity [1]						
Mild	xx	xx (xx.x%)	xx	xx (xx.x%)	xx	xx (xx.x%)
Moderate	xx	xx (xx.x%)	xx	xx (xx.x%)	xx	xx (xx.x%)

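### The urgent DMC review trigger in Protocol 15.3 omits the Energizer, so a non-fatal SAE rated related only to the Energizer has no stated DMC deadline before the next scheduled meeting

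*Protocol*

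**What the plan says.** Protocol 15.3 says that the DMC reviews all AEs regularly and adds ad hoc "reviews occurring within 5 working days of sponsor notification". The events that call for such a review are "any subject death or SAE related to the implant procedure, explant procedure, implant device, or stimulation". The sentence describes this as following the DMC Charter. The same section lists what the independent adjudicator receives, including "A list of potential risks associated with the implant device, implant procedure, explant procedure and stimulation therapy". Both lists have the same four sources.

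The causality sections use five. Protocol 15.1 rates each AE for its relationship "to the implant device, implant procedure, explant procedure, Energizer and stimulation therapy", and 15.2.2 states: "The relationship of all AEs to the implant procedure, explant procedure, implant device, Energizer and stimulation will be evaluated by Co-PIs". The primary SAP (CLP-004, Section 9.1) and the long-term SAP (CLP-008, Section 7.1) use the same five.

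Section 7.2.3 describes the Energizer as a collar that is worn externally and not implanted. Section 16.6 lists foreseeable harms that it could cause, such as "Asphyxiation caused by misuse of Energizer".

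Section 18.2.5 schedules DMC meetings at 15, 30, 45 and 60 subjects in Stage 1 and every 3 months during Stage 2 enrollment. After that: "Following completion of Stage 2 enrollment, the DMC will meet once every 6 months".

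**The concern.** The trigger sentence decides which serious events reach the independent committee within days and which wait for a routine meeting. One of the five sources that investigators are told to assess is absent from it, and that source carries serious named hazards in the sponsor's own risk analysis. The Energizer sits on the neck, transmits radio-frequency energy, and is used for regular charging; Sections 11.5.4 and 11.9 call for weekly charging. Exposure therefore recurs throughout follow-up.

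If the sentence is followed literally, a serious burn from the collar is treated as less urgent for the DMC than an SAE of the same seriousness attributed to the implant. No passage gives a reason for that difference. The revision history records the Energizer being added to the AE relationship options in Revision I and as a relationship classification in Revision L. That history fits a list in 15.3 that was not brought along, rather than a decision to exclude it.

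**Working it through.** No sample size, power or alpha figure bears on this point. The check compares the lists and then works out the waiting time.

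**1. Sources, side by side**

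| Source | 15.1 and 15.2.2 | CLP-004 9.1, CLP-008 7.1 | 15.3 DMC trigger | 15.3 adjudicator's list |
|---|---|---|---|---|
| Implant procedure | yes | yes | yes | yes |
| Explant procedure | yes | yes | yes | yes |
| Implant device | yes | yes | yes | yes |
| Stimulation | yes | yes | yes | yes |
| Energizer | yes | yes | **no** | **no** |

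**2. Can implant device be read to include the Energizer?** No. Section 7.2.3 says it is not implanted, and 15.1 and 15.2.2 list the two separately. Section 15.2.2 does define a broader class of device-related events, but the trigger does not use that term.

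**3. Which Section 16.6 harms could be rated Energizer-only?**
- Electrocution from malfunction or misuse of the Energizer or Wireless Charger: yes.
- Tissue damage from radio-frequency exposure or a burn: yes.
- Asphyxiation from misuse: yes.
- Tissue damage from unsafe stimulation levels delivered through an Energizer malfunction: this would plausibly also be rated related to stimulation, and would then trigger review.

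**4. Waiting time.** For an SAE that meets the trigger, the limit is 5 working days from sponsor notification, about 7 calendar days. For one that does not, the longest wait is one scheduled interval. With fixed intervals and an event at a random time, the mean wait is half the interval.

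| Period | Interval (18.2.5) | Longest wait | Mean wait |
|---|---|---|---|
| Stage 2 enrollment | 3 months | about 91 days | about 1.5 months |
| After Stage 2 enrollment | 6 months | about 183 days | about 3 months |

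Relative to 7 days, the longest waits are 91/7 = 13 and 183/7 = about 26 times as long.

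In Stage 1 the interval depends on accrual. Section 11.11 plans 60 subjects in 8 months, or 60/8 = 7.5 per month. With even accrual (an assumption), 15 subjects take 15/7.5 = 2 months. For the enrollment pause of about 6 months, 18.2.5 names only the end-of-Stage-1 interim review.

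**5. SAP overview tables**

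| Energizer row or block | CLP-004 Table 14.1.3.1 | CLP-008 Table 14.8.3.1 |
|---|---|---|
| Not related, related, indeterminate | absent | absent |
| By maximum severity | absent | present |
| SAE | present | present |

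The severity blocks of Table 14.1.3.1 end with "Explant Procedure AE by maximum severity" and include none for the Energizer. Energizer-related AEs by system organ class and maximum severity are reported separately in Tables 14.1.3.7 and 14.8.3.6.

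**The case against.** The strongest objection is that 15.3 summarises a Charter that is not among the documents. Sections 17.3 and 18.2.5 and both SAPs also refer to that Charter, and Revision K changed the meeting frequency to match it. A wider trigger there cannot be excluded. This stands as a limit on the practical consequence: a reader might infer that Energizer SAEs will in fact wait months, and the documents show only that the protocol sets no earlier deadline. It does not remove the inconsistency. If the Charter has the same four sources, both need changing; if it has five, the protocol misstates it.

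Other safeguards are real. Every SAE reaches the sponsor within 24 hours (15.4). The sponsor reviews each AE, FDA and IRB reporting apply, device deficiencies are investigated (18.2.3), and the sponsor may terminate at once for unreasonable device risk (18.7). Section 17.3 says that the DMC monitors safety continuously through Stages 1 and 2 and can stop the study at any time. So a reader should not infer that an Energizer hazard would go unexamined. But none of these sets a deadline for DMC review. The route for unanticipated effects may not help either: under 15.2.3, an event consistent with the Section 16 risk information is classed as expected, and these harms are listed there.

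Four further inferences go too far:
- **That the 6-month wait applies to the whole 252-week open-label period.** The 6-month interval starts when Stage 2 enrollment is complete. Open-label follow-up starts after each subject's own Week 12, so for earlier subjects it overlaps the 3-month schedule.
- **That a hazard would affect all implanted subjects at once.** Nothing says so. Section 16.6 attributes electrocution partly, and asphyxiation wholly, to misuse, which can be an isolated event.
- **That the adjudicator would judge such events without the relevant information.** The adjudicator acts only when investigator and sponsor disagree on seriousness or causality, receives the clinical record, and may ask for more.
- **That Energizer AEs go unreported.** The dedicated tables already cover most of that content.

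**Conclusion.** The point holds in a limited form. Section 15.3 works with four of the protocol's five causality sources, both for the urgent DMC trigger and for the adjudicator's risk list. A non-fatal SAE rated related only to the Energizer therefore has no stated DMC deadline before the next scheduled meeting, compared with 5 working days for the other four sources.

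The conclusion takes 15.3 as the operative rule and assumes that meetings keep to the 18.2.5 schedule. Fatal events are outside it, as are events also rated related to another listed source. No endpoint or inference is affected. The group of events is narrow and probably rare, but the named harms are serious, no reason is given for treating them differently, and the correction is cheap. It should be made. The gap in the overview tables is minor.

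**What to change.** 1. In Protocol 15.3, add the Energizer, with its Wireless Charger, to the SAE sources that trigger the ad hoc DMC review.
2. In the same section, add Energizer risks to the list supplied to the independent adjudicator.
3. Check the DMC Charter and reconcile it with 15.3, so that both use the five sources of 15.1 and 15.2.2.
4. As a minor consistency change, add Energizer rows to the not-related, related and indeterminate blocks of Tables 14.1.3.1 (CLP-004) and 14.8.3.1 (CLP-008), and an Energizer severity block to Table 14.1.3.1.

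The cost is wording in the protocol, in the Charter if it has the same gap, and in two table shells, plus a rare extra ad hoc review. No new data are needed, because the Energizer relationship is already assessed for every AE.

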15.4 Guidelines for Reporting of AEs

All AEs, regardless of seriousness or relationship to the investigational device, will be recorded in the EDC system and will include event description, date of onset, investigator's assessment of severity, relationship to investigational device, and date of resolution/stabilization of the event. All AEs will be followed through end of the study or through study exit of individual subject.

Any pre-existing medical condition that is present at the time of Screening will not be reported as an AE, unless there is a worsening of that condition. The occurrence of diagnostic or elective

surgical procedures for a pre-existing condition will not be recorded as an AE, unless the condition becomes more severe or results in an AE.

Whenever possible, diagnosis or single syndrome should be reported instead of symptoms. The investigator should specify the date of onset, severity, action taken with respect to the investigational device, corrective treatment/therapy given, additional investigations performed, outcome, and his/her opinion as to whether there is a reasonable possibility that the AE was caused by the investigational device.

The investigator should take appropriate measures to follow all AEs until resolution or until progression has been stabilized, or until study exit, to ensure the safety of the subjects. If the AE continues beyond the last planned visit per protocol and/or the subject withdraws from the study, clinical investigators should follow the subjects according to standard of care.

All AEs must be reported to sponsor based on the following timeline:

Type of AE	Reporting Schedule to Sponsor
Subject death	Within 24 hours from becoming aware followed by a written report within 2 working days
SAE (SAE/SADE/UADE/USADE)	Within 24 hours from becoming aware followed by a written report within 4 working days
Device-related AE	Within 24-48 hours from becoming aware

The investigator will report the above to the reviewing IRB per the IRB's guidelines. The study sponsor is responsible for reporting safety events to the FDA as required per 21 CFR 812 and to IRB per the IRB's guidelines.

All SAEs (SAE/SADE/UADE/USADE) will be followed until satisfactory resolution, until the investigator deems the event to be chronic, or until the subject exits the study. Other supporting documentation of the event may be requested by the sponsor and should be provided as soon as possible.

16 RISK/BENEFIT ASSESSMENT

16.1 Assessment of Risks for the Proposed Investigation

VNS therapy for the treatment of RA has risks associated with the surgical procedure required to implant the stimulation device and with the electrical stimulation itself. The risks are discussed in detail later in this section. These risks have been evaluated in animal studies, in the proof-of-concept study in RA subjects implanted with the Cyberonics VNS Therapy System (SPM-005), and in the pilot study of the SetPoint System (SPM-008) (see Section 7.3). The risks are potentially severe, and the likelihood of AEs related to the device is only partially understood. Risk mitigation procedures include careful selection of eligible subjects, the use of specialized, highly experienced investigators, including neurosurgeons with previous surgical experience

using approved VNS devices and rheumatologists with extensive clinical trial experience. A formal training program will be required for all surgeons who participate in this study to ensure adequate experience. Device programmers will undergo formal training as well.

The assessment of risk is informed by long-term follow-up studies of patients who have had FDA approved VNS devices implanted for treatment of drug refractory epilepsy or treatment resistant depression. These studies reveal complication rates of < 5%. Complications include post-operative infections, device failure due to lead fracture, hoarseness, dysphasia, dysphonia, and vocal cord paralysis. In rare instances, the device had to be removed (Aalbers 2015). VNS devices were approved for use 20 years ago, and more than 100,000 VNS devices have been implanted in more than 80,000 patients (Revesz 2016). As such, there is an extensive safety record for VNS devices in non-immunosuppressed patients with seizure disorders or depression.

It is possible that the likelihood of infection for an implanted VNS device will be higher in an RA patient population given the disease causes inflammation and that immunosuppressive drugs are routinely prescribed, such as methotrexate, steroids and TNF inhibitors.

